15.2 Source Documents

The source documents for the trial data will be identified before the study start by the CI. It is anticipated that the majority of source data (medical progress notes and letters, tests and investigations) will be filed in the individual patients medical records. Any deviation from source data being present in the medical notes will be identified and documented for the duration of the study. The eCRF and source documents must be available at all times for review by the Sponsor's clinical trial monitor, auditors and for inspection by the Medicines Health Regulatory Agency (MHRA). The accuracy of eCRF data will be verified by review of the source documents and details will be provided in the study monitoring report for each study site.

Information should be entered legibly. If there is an error in the notes, it should be crossed through with a single line in such a way to ensure that the original entry can still be read. The correct entry should be clearly inserted. The amendment should be initialled and dated by the person making the correction immediately. Overwriting or use of correction fluid will not be permitted.

15.3 Data collection tool

Case Report Forms (CRFs) will be designed by the CI in liaison with Imperial College clinical Trials Unit (ICTU) and the final version will be approved by the Sponsor. All data will be collected on an electronic CRF (eCRF) *via* InForm database system. The eCRF will be designed in accordance with the requirements of the clinical trial protocol and will comply with regulatory requirements. Local personnel will be trained on the InForm system. Access will be restricted to site personnel, trial managers, trial monitors, data management team. Personnel will have individual logon and passwords. It is the Investigator's responsibility to ensure the accuracy of all data entered and recorded in the eCRFs. The Delegation of Responsibilities Log will identify all trial personnel responsible for data collection, entry, handling and managing the database and the data entered in the eCRF. Trial monitors will check the accuracy of the eCRF data against source documents.

The majority of source data (medical letters and progress notes, results of tests and investigations) will be filed in the individual patients' medical records. The data specifically relative to the study including questionnaire data, patient activity diaries, and readings from activity monitors/oxymeters will be entered directly onto the CRF.

All the questionnaires used in this study have been previously standardized and validated (14-19). Similarly, data obtained from the oxymeter reading and Sensewear armband have been validated as described in the literature (22-23). The patient activity diary has previously been validated against activity monitors in patients with chronic lung disease (23,24).

In order to maximize completeness of data, patients will be called at the end of each week. If they have forgotten to wear the activity monitor and/or the oxymeter for the allocated time, they will be asked to make up for the lost days over the following week. Patients will also be encouraged to continue filling in their daily activity diaries. The accuracy of the CRF data will be verified by review of the source documents.

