- Provide a Sensewear armband for patients to wear during the second week (5+2 days) of each of the two week treatment periods;
- Provide oxymeter for patients to wear for 48 hrs during the second week of each two week treatment periods (on oxygen and on no oxygen);
- Supply a diary of daily activities and instructions on completion by patients during the two weeks until the next visit (Visit 3);
- Dispense treatment based on randomisation allocation.
- The next study visit will be set up within two weeks of the baseline visit.

10.5 Crossover Visit – Visit 3 in Week 2

At Visit 3, patients will be asked to:

- Pulse oximetry at rest on room air;
- Concomitant medication review;
- AE assessment;
- Global assessment of change in walking ability and breathlessness (18);

- Ask patients to submit daily activity diary relating to the previous two weeks, Sensewear armband given during the baseline visit (visit 2) and therefore related to the past two weeks;
- Ask patients to submit their 48 hrs oxymeter readings, provided at the baseline visit;
- Complete study questionnaires including K-BILD questionnaire (14), Shortness of Breath Questionnaire (SOBQ) (15), St George's Respiratory Questionnaire (SGRQ) (16), Hospital Anxiety and Depression Scale (HDAS) (18),
- Ask patients to complete diary of daily activities during the following two week treatment period until the next visit (visit 4);
- Provide Sensewear armband for patients to wear during the second week (5+2) of the two weeks of the final treatment period;
- Provide oxymeter for patients to wear for 48 hrs during the week when the Sensewear armband is worn;
- Cross-over to the alternative treatment.

10.6 End of Treatment Visit – Visit 4 in Week 4

At Visit 4, patients will be asked to undertake:

- Pulse oximetry at rest on room air
- Concomitant medication review
- AE assessment
- Global assessment of change in walking ability and breathlessness (19)
- Ask patient to submit daily activity diary, Sensewear armband, and 48 hrs oxymeter reading related to the final two week treatment;
- Complete study questionnaires including K-BILD questionnaire (14), Shortness of Breath Questionnaire (SOBQ) (15), St George's Respiratory Questionnaire (SGRQ) (16), Hospital Anxiety and Depression Scale (HDAS) (18).

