10.9 Summary of study Assessments

Questionnaires: As previously stated, the primary outcome will be the change in the King's Brief Interstitial Lung Disease (K-BILD) total health status score (14). Participants will be asked to complete this questionnaire, at screening and baseline visit (Visit 1 and Visit 2) and at the end of each two-week period (visit 3 and 4). In the same points (visit 2, 3 and 4) they will also be asked to complete the Shortness of Breath Questionnaire (SOBQ - University of California, San Diego) (15), a widely validated index, designed to assess activity-related dyspnoea, as well as a questionnaire evaluating Quality of Life (St George Respiratory Questionnaire – SGRO) (16) and the Hospital Anxiety and Depression scale, both validated in ILD (18).

At the end of the third and fourth visit, participants will also be asked to make a global assessment of change in their walking ability and in their breathlessness on walking as “worse”, “about the same” or “better” (19), when compared to the previous two weeks.

Activity assessment: During the second week of each of the two week periods of the study treatment, patients will be asked to wear an activity monitor during waking hours, the Sensewear armband (Bodymedia - Pittsburgh, Pennsylvania), which measures energy expenditure, daily number of steps, and time spent at different levels of physical activity. Sensewear-derived measurements are sensitive and repeatable in chronic lung disease patients (22). The monitor is currently used at the RBH in a number of projects in COPD, and [name], one of this proposal's co-applicants, has established expertise in the use and assessment of activity measures. Patients will also be asked to complete a diary of daily activities as measure of physical activity, by using the modified diary method of Follick *et al* () (23, 24). Participants will be asked to complete this diary at least 3 times daily, recording the activity undertaken for the majority of each two hour block, in addition to specifying whether oxygen cylinders were used. In addition, total hours of outings each day will be recorded.

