Oxygen Cylinder Use: will be expressed as number of cylinders used and as hours of use from self-reported data; patients will also be asked to write down the time of use of oxygen canisters for the two days a week when they will also be wearing the portable oxymeter, so as to correlate the two. At the end of the two weeks on oxygen, each patient will also be asked to fill in questionnaires about the number of cylinders fully and partially used and the number of unused cylinders.

Oxygen saturation: two days a week for each of the four weeks, patients will also be asked to wear a portable oxymeter, to assess oxygen saturation for 48 continuous hours. Measures of continuous oxygen saturation will also allow control for self-reported use of ambulatory oxygen.

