13.2 Accountability procedure for the IMPs

Ambulatory oxygen will be provided by the existing structure using the oxygen companies as described in Section 14.1 above. At the end of the study period, patients will continue on ambulatory oxygen as part of their standard care, and there will therefore be no returned IMP. If the patients are randomised to start on oxygen on the first two weeks of the four week trial period, the company will be asked to remove any unused oxygen cylinders prior the two weeks "off" oxygen.

To determine oxygen use during the study and in particular during the 2 weeks when patients are randomized to be on treatment, patients will be asked to keep a daily diary recording the number of hours spent using oxygen. The flow will be fixed at the optimal flow established at the baseline 6MWT on O₂ at the study entry. Investigators will also ask the relevant oxygen company to provide the number of cylinders delivered to the patient per

week along with the number of any unused cylinders at the end of the two weeks on oxygen, where possible.

The pharmacy hospital department will not be responsible for the provision and management of study IMP.

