17.2.2 Secondary endpoints

- a) Dyspnoea scores as assessed by the San Diego shortness of breath questionnaire (15)
- b) Global assessment of change in walking ability and exertional breathlessness as better, the same or worse
- c) Quality of life as assessed by SGRO (16) and the hospital anxiety and depression score (18)
- d) Sense wear activity monitor measures of daily number of steps walked, daily expenditure and time spent at different levels of activity
- e) Continuous oxygen saturation for 48 hours at weekly intervals

- f) Individual questions specifically related to activity from both the K-BILD and the SOBQ questionnaires

All of the above are continuous variable and will be analysed as such at least in the first instance. However, categorical analysis will also be performed, when appropriate on reviewing the distribution of the data.

Qualitative assessment of the impact of ambulatory oxygen. With regards to the qualitative arm of this study, we plan to investigate patients' and their carers' personal perspectives on how the ambulatory oxygen has affected their day to day life by conducting semi-structured open-ended interviews in a subset of 20 patients and their carers at the end of the study. Based on the information we gained from informal conversations with ILD patients already using ambulatory oxygen, a topic guide will address a series of issues identified as important, including practical barriers to optimal oxygen usage, practical, social and psychological difficulties encountered, concerns about dependency, and views on the information required prior to ambulatory oxygen prescription. The interviews will also explore patients' (and carers') experience of participating in the trial and recruited at RBH in order to inform the definitive multi-centre trial. Field notes will be written after each interview to aid reflexive analytical processes (25). Individual feed-back on how the system and the service could be improved will assess how the needs of patients and their future involvement can be incorporated into the design of more patient centred devices.

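### Section 15.3 lets missed armband or oximeter days be made up in the following week without limiting this to the same treatment period, so days missed in week 2 are recorded on the opposite treatment.

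*Protocol*

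**What the plan says.** Section 15.3 describes how device data are to be kept complete: "patients will be called at the end of each week", and if the activity monitor or oximeter was not worn as planned, "they will be asked to make up for the lost days over the following week". It does not restrict the make-up to the same treatment period, and it does not say how a made-up day is labelled.

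The armband is scheduled late in each period. Section 10.4 has staff "Provide a Sensewear armband for patients to wear during the second week (5+2 days) of each of the two week treatment periods", and section 10.9 agrees: "During the second week of each of the two week periods of the study treatment". Section 6.1 states that no wash-out is needed, and section 6.1.4 has patients switch to the alternative after the first two weeks. Section 13.2 has unused cylinders removed before the off-oxygen weeks for patients who had oxygen first. For the time after week 4 it says: "At the end of the study period, patients will continue on ambulatory oxygen as part of their standard care".

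Devices are handed in at Visit 3 and provided again for the final period (section 10.5). At Visit 4 they are handed in and none is issued (section 10.6).

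The oximeter schedule is given in more than one way. Section 10.4 says "Provide oxymeter for patients to wear for 48 hrs during the second week of each two week treatment periods". Section 10.9 says "two days a week for each of the four weeks", and section 17.2.2 lists the endpoint as "Continuous oxygen saturation for 48 hours at weekly intervals".

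**The concern.** In a two-period crossover, each measurement has to belong to the treatment in force when it was taken. Here the wear week is the last week of the period and the shortfall is found at the end of that week. The following week is then always outside the period being measured. For week 2 it is the first week of the opposite treatment.

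The endpoints exposed are d (steps, energy expenditure, time at activity levels) and e (48-hour saturation) in section 17.2.2. They are secondary, but they carry weight. The trial is unblinded with a patient-reported primary endpoint, and section 6.1 proposes to use objective secondary measures to argue that a K-BILD benefit is not a placebo effect. The home-recorded armband and oximeter data are the objective measures taken during treatment, since the walk tests are done only at screening and baseline. Mixing conditions pulls the two means together and weakens that argument.

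**Working it through.** The protocol gives no figure to reproduce here, so the check compares the schedule with the make-up rule and then sizes the effect under stated assumptions.

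**Step 1. Condition in the week after each armband week** (sections 6.1, 6.1.4, 10.4 to 10.6, 13.2, 13.6)

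| Sequence | Wear week | Intended | Following week | Match? | Device available? |
|---|---|---|---|---|---|
| Oxygen first | 2 | on | week 3, off | no | yes, provided at Visit 3 |
| Oxygen first | 4 | off | week 5, post-trial oxygen | no | no, handed in at Visit 4 |
| No oxygen first | 2 | off | week 3, on | no | yes, provided at Visit 3 |
| No oxygen first | 4 | on | week 5, post-trial oxygen | same condition, outside the trial | no, handed in at Visit 4 |

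Both week-2 rows are wrong and also feasible. The week-4 rows conflict with section 10.6, because no device is left with the patient after Visit 4.

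**Step 2. Oximeter.** Under the second-week schedule (section 10.4) the table applies unchanged. Under the weekly schedule (section 10.9), days missed in weeks 1 and 3 are made up in weeks 2 and 4, which are on the same treatment. Only make-up after weeks 2 and 4 leaves the period.

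**Step 3. Effect for one patient.** Let f be the share of scheduled days in one period that is made up under the other condition and counted towards the earlier period. That period's mean becomes (1 − f) × intended + f × opposite, and the other period is clean. The share of the true contrast kept is 1 − f.

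- f = 1/7: 6/7 = 86%
- f = 2/7: 5/7 = 71%
- f = 3/7: 4/7 = 57%
- one of two oximeter days: 1/2 = 50%

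The values of f are assumptions.

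**Step 4. Effect on the trial average.** If a share p of patients is affected in this way and the true contrast is the same in all patients, the average loss is p × f. With f = 3/7:

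- p = 5%: 0.05 × 3/7 = 2.1%
- p = 20%: 0.20 × 3/7 = 8.6%

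This is about 2% to 9%. The values of p are also assumptions.

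**Step 5. After the fix.** If make-up days must stay in the same period or be left missing, no row of the table is recorded under the wrong condition, and this source of dilution disappears.

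**Step 6. Number of oximeter recordings.** One 48-hour recording per period (sections 10.4 and 10.5, Appendix 1) gives 2 per patient. Two days in every week (section 10.9; section 13.5 and endpoint e in section 17.2.2 also point to weekly recording) gives 4.

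**The case against.** Several points on the other side have force.

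- **Only missed days are affected.** Section 17.4.2 expects little missing data, and K-BILD does not depend on the devices. This stands, and it is why the trial-level size is modest.
- **Misattribution is not stated.** No section says that a week-3 day counts as period 1, and the diary records cylinder use, so days could be analysed by actual condition. An analysis plan not shown here may do so. This stands in part: such a plan could relabel or discard the days, but the instruction to collect them after the crossover is in the protocol, and the lost week-2 data would not be recovered.
- **The visit window may give slack.** Section 10.1 allows 7 days either side, so a delayed Visit 3 could keep make-up in the same period. The protocol does not link the two, and section 10.4 sets the next visit within two weeks of baseline. This mitigates but does not cure.

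A reader might also infer more than the documents support.

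- **Contamination in both periods.** For an oxygen-first patient with 3 of 7 days made up each time, this would leave 4/7 − 3/7 = 1/7 of the contrast. It needs wear in week 5, for which section 10.6 leaves no device. It shows a conflict between sections 15.3 and 10.6, not a likely outcome.
- **Oximeter schedules that sites cannot both satisfy.** Two days in each of four weeks can include the 48 hours in each second week, and Appendix 1 asks only for 48 hours within the two-week period. The texts differ on how many recordings are wanted; they are not mutually exclusive.

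**Conclusion.** The concern holds for days missed in week 2. Followed as written, section 15.3 moves them into week 3 on the opposite treatment in both sequences. If they are then counted towards period 1, secondary endpoints d and e are biased towards no difference. An affected patient keeps 86% to 57% of the true contrast for 1 to 3 of 7 days made up, and the average loss is about 2% to 9% if 5% to 20% of patients make up 3 of 7 days. These figures rest on assumed rates of missed wear, equal true contrasts across patients and attribution to the earlier period.

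Make-up after week 4 is chiefly an inconsistency with section 10.6. Oximeter make-up after weeks 1 and 3 under the weekly schedule is harmless. The documents do not support saying that the objective endpoints as a whole are recorded under the wrong condition. The primary endpoint is untouched, and the placebo argument in section 6.1 is weakened, not invalidated. This should be fixed because the remedy is cheap and the lost days cannot be recovered later, but it does not threaten the main result.

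**What to change.** In section 15.3, state that make-up days must fall before the crossover visit (period 1) or the end-of-treatment visit (period 2) of the same treatment period, and that days not made up by then are missing. Place a reminder call early in the second week, while there is still time to act; the end-of-week call comes too late for the armband. State that each recorded day is attributed by date to the treatment in force, so that no day after the crossover counts towards the earlier period.

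Separately, choose one number of oximeter recordings and use it in sections 10.4, 10.5, 10.9, 13.5 and 17.2.2 and Appendix 1.

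The cost is a change of wording and the timing of a telephone call. The downside is a few more incomplete wear-weeks.

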15.4 Data handling and analysis

The InForm system (database) provided by the Imperial Clinical Trials Unit (ICTU) will be used for data entry and storage. The ICTU will design and build the electronic Case Report Forms (eCRFs) and validation rules for data entry to ensure the data can be collected accurately and stored securely. User support is provided during the life cycle of the trial to deal with forgotten passwords, questions on how the system works and any perceived issues with the system. ICTU database team also provides assistance with ad hoc report development and research data extracts for safety committees, final reports or as requested.

The service is provided using InForm Integrated Trial Management (ITM) System, a web-based data entry system which builds an Oracle database for each individual clinical trial. InForm, supplied by Oracle | Phase Forward, is widely used across the pharmaceutical industry. The databases are hosted on Imperial College's infrastructure and can be analyzed using an inbuilt reporting package, Cognos.

Central Designer, also supplied by Oracle | Phase Forward, is the tool used to design and build the eCRFs (electronic case report forms) and data entry rules for trials.

The quality of data entry will be checked at regular intervals throughout the trial. The analysis will be performed by the CI and the PIs in collaboration with the Trust statistician and will be performed independently of data entry.

16 Archiving arrangements

The trial documents (including the Trial Master File (TMF), Case Report Forms (CRFs), Informed Consent Forms along with the trial database) will be kept for a minimum of five years. They will be stored in locked offices within the Royal Brompton and Harefield NHS Foundation Trust site for the duration of the study. The Chief Investigator is responsible for the secure archiving of trial document. The trial database will also be kept electronically on the Trust computer network, for a minimum of five years.

The approved repository for longer retention of local materials for studies that involve RB&HFT patients is **Box-It Storage UK**. The study documentation will be prepared for archiving by the research team in line with the Research Office Archiving SOP and the transfer will be arranged by the Research Office.

17 Statistical design

17.1 Statistical input in trial design

Data analysis will be performed by the Chief Investigator (CI) with the input of the Trust statistician, [name], who will ultimately be responsible for the accurateness of data analysis. All data will be analysed with intention to treat and patients who do not adhere to the study protocol correctly will be excluded as "per protocol" analysis.

17.2 Endpoints

17.2.1 *Primary endpoints*

The primary endpoint will be the change in health status, as measured by the K-BILD questionnaire (14). It is a continuous variable.

17.2.2 Secondary endpoints

- a) Dyspnoea scores as assessed by the San Diego shortness of breath questionnaire (15)
- b) Global assessment of change in walking ability and exertional breathlessness as better, the same or worse
- c) Quality of life as assessed by SGRO (16) and the hospital anxiety and depression score (18)
- d) Sense wear activity monitor measures of daily number of steps walked, daily expenditure and time spent at different levels of activity
- e) Continuous oxygen saturation for 48 hours at weekly intervals

- f) Individual questions specifically related to activity from both the K-BILD and the SOBQ questionnaires

All of the above are continuous variable and will be analysed as such at least in the first instance. However, categorical analysis will also be performed, when appropriate on reviewing the distribution of the data.

Qualitative assessment of the impact of ambulatory oxygen. With regards to the qualitative arm of this study, we plan to investigate patients' and their carers' personal perspectives on how the ambulatory oxygen has affected their day to day life by conducting semi-structured open-ended interviews in a subset of 20 patients and their carers at the end of the study. Based on the information we gained from informal conversations with ILD patients already using ambulatory oxygen, a topic guide will address a series of issues identified as important, including practical barriers to optimal oxygen usage, practical, social and psychological difficulties encountered, concerns about dependency, and views on the information required prior to ambulatory oxygen prescription. The interviews will also explore patients' (and carers') experience of participating in the trial and recruited at RBH in order to inform the definitive multi-centre trial. Field notes will be written after each interview to aid reflexive analytical processes (25). Individual feed-back on how the system and the service could be improved will assess how the needs of patients and their future involvement can be incorporated into the design of more patient centred devices.

